Participant Recruitment, Screening and Randomization:

CC's Center for Neurological Restoration (CNR) manages 6,000+ PD patients; each patient typically has semi-annual neurology visits which include a complete MDS-UPDRS III evaluation. UU's Movement Disorders Program manages 2,000+ PD patients. Their respective Directors, Drs. [name] (Cleveland) and [name] (Utah), will lead their medical teams to screen in recruiting for this project and will complete MDS-UPDRS III clinical evaluations, blinded to group assignment. The pragmatic clinical trial design, with exercise at home and relatively few visits to the study site, will minimize travel burden, easing recruitment and facilitating recruitment of a racially and socio-economically diverse patient group.²³ It is anticipated that study sites will enroll an equal number of participants. Adults with idiopathic PD who meet inclusion criteria and cleared for exercise will

be randomized to either the home exercise or UCC group, using a permuted block randomization stratified by site, with random block sizes of 8, 10, or 12 for the first 8 blocks at each site, and 4, 6, or 8 subsequently, preloaded into a secure and shared RedCap electronic data management system developed at CC. Both sites have effectively utilized RedCap across in previous multi-site clinical trials,²⁴⁻³¹ and clinical programs. Figure 1 depicts study flow. Total study participation time is projected to be 12.5 months, including ~2.5 weeks for cycle delivery and completion of initial Comprehensive Assessments (On-/Off- meds).

As shown in Figure 1, three Comprehensive assessments of motor and non-motor function will be conducted for all participants. Comprehensive (90 mins) assessments (Table 1) will be overseen by Drs. [name] and [name], and will be completed at project enrollment (On- and Off-medication), 6 months (Off-medication), and 12 months (Off-medication). Visit windows will be within \pm 10 days of their nominal dates. Participants will be reimbursed for time and travel expenses of \$50 for each assessment. All clinical and self-report data will be entered into the RedCap database (see Data and Safety Monitoring). Each site's biomechanical data from the iPad will be uploaded securely, with encryption, to the CC HIPAA-compliant cloud instance (ClearData), processed in the cloud, and integrated into the [name] lab's on-premises, firewall protected, server.

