- iii. Working memory/set switching: the ratio of time to complete the Trail Making Test B to time to complete the Trail Making Test A.

Descriptive/exploratory motor outcomes are:

- i. Cardiovascular fitness: Six Minute Walk Test distance;
- ii. Postural stability:
 - a. Balance Error Scoring System (BESS) double leg area
 - b. Balance Error Scoring System (BESS) tandem area
 - c. Balance Error Scoring System (BESS) double leg volume
 - d. Balance Error Scoring System (BESS) tandem volume
- iii. Total self-reported falls during the one-year observation period.

Descriptive/exploratory non-motor outcomes are:

- i. Movement Disorder Society Unified Parkinson's Disease Rating Scale Part I: Non-Motor Aspects of
- ii. Experiences of Daily Living (nM-EDL)
- iii. Movement Disorder Society Unified Parkinson's Disease Rating Scale Part II: Motor Aspects of Experiences of Daily Living (M-EDL)

iv. Movement Disorder Society Unified Parkinson's Disease Rating Scale Part IV: Motor Complications. The latter two scales are classified as non-motor rather than motor outcomes because they focus on patient-reported experience of functional and social impacts of the effects of motor symptoms rather than on the symptoms themselves.

Analysis Sets

The inferential and safety analysis set will consist of all randomized patients. The descriptive/exploratory analysis set will consist of all randomized patients who complete baseline procedures for initiating randomized treatment and follow-up, and for whom study follow-up is initiated. Descriptions of baseline variables will use all available data in the inferential and safety analysis set. Inferential and safety outcomes will be analyzed using the inferential and safety analysis set in accordance with the strict intention-to-treat principle, under which all randomized patients are included in analyses in accordance with their randomized treatment assignments, regardless of their post-randomization experience including treatment and dropout from treatment or study. Descriptive/exploratory outcomes will be analyzed using the descriptive/exploratory analysis set.

Missing Data

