The distributions of baseline variables will be summarized, overall and by treatment group, by frequency distribution for dichotomous and other categorical factors, mean and standard deviation for reasonably symmetrically distributed quantitative variables, and Tukey five-number summaries (median, quartiles, extrema) for substantially skewed variables. We will also examine boxplots, histograms and kernel density estimators for continuous variables, and use standardized mean differences for continuous variables and categories of nominal and ordinal variables to describe balance of the randomized treatment groups.

Outcome description and distributional assessment

All prespecified outcomes are quantitative or potentially treatable as such depending on the degree to which their full scales occur in our study population. We will thus describe each initially as indicated above for quantitative baseline variables, overall and by treatment \times time combinations, including visually using grouped boxplots and kernel density estimators. To assess compatibility with the assumptions of the planned analytic approach, for each outcome we will use restricted (equivalently, residual) maximum likelihood (REML) estimation to fit preliminary mixed models with fixed effects of randomized treatment, visit, and their interactions, and with unrestricted covariance matrices -- thus allowing within treatment and visit variability to change over time and accounting for arbitrary correlations between measurements of the outcome in the same patient at different visits. These models will not be used to estimate treatment effects, but only to assess the compatibility of their residuals with the requisite distributional assumptions about random noise to support validity of fixed effect estimates and tests from the planned inferential analyses.

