Once the scale of analysis and analytic approach have been chosen for outcomes incompatible with the prespecified default model, a covariance structure will be selected for each non-multinomial analysis by comparing Schwarz' Bayesian Information Criterion (BIC) after fitting the unconstrained fixed effects model above using the following six choices: time series homogeneous and heterogeneous order one autoregressive AR(1), order one antedependence, homogeneous and heterogeneous compound symmetry, and unrestricted. The homogeneous AR(1) will be considered the default if it yields close to the minimum BIC; otherwise, the structure with minimum BIC will be used. Residuals from the above saturated fixed effects model with the selected covariance structure will then be checked as above to confirm adequacy of the transformation or generalized linear mixed model.

Treatment effect estimation and testing

Assuming required assumptions are reasonably met, missing data will be multiply-imputed with 50 imputations, as described above, after any transformations of all outcomes to the respective scales determined for analysis. Treatment effects will then be estimated and tested by fitting mixed models, also as described above, on the original or transformed scale, but assuming equally spaced visits and linear time effects, to each imputed full data set. Estimates of the annual rate of change of the outcome variable within each treatment group, and of the treatment effect as their difference, with respective standard errors, will be obtained from each imputation and combined over all imputations using Rubin's standard method, yielding overall point estimates of the rates in each group and the difference in rates between the home Peloton-based exercise and usual care groups (i.e., the treatment effect), with respective overall 95% confidence intervals. Statistical significance of the treatment effects and of temporal change within each group will be tested using Wald statistics. Point and interval estimates on a transformed scale will be back transformed and reported and interpreted on the scales of the original measurements as differences between model-fitted (“predicted”) values of the outcomes for participants beginning with the same baseline value of the outcome measure but assigned to the two groups, for a selection of baseline percentiles of the outcome measure (e.g., 5, 10, 25, 50, 75, 90, 95)..

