For inferential outcomes for which statistically significant treatment effects are found, in either direction, we will further explore the nature of the treatment effect. For the primary outcome and any descriptive/exploratory outcomes that are also indices of multiple Parkinson's disease manifestations and that exhibit clinically relevant differences between treatment group, we will summarize and compare subscores associated with different symptom groups, e.g., speech and facial expression, hand movements, lower body movements, tremor. For any outcome with statistically significant treatment effect, we will examine the effect in a model saturated for treatment and time, within which we will separately estimate and test equality of the changes within each six-month period, i.e., test for nonlinearity over the one-year duration of treatment and compare treatments with respect to the changes within each six-month period and over the full year of treatment.

Sensitivity analyses

We will employ several sensitivity analyses to test the dependence of substantive results on our modeling assumptions. Our planned analyses rely on randomization to protect against confounding by baseline differences between the treatment groups. We will compare treatment groups on the baseline variables mentioned above and perform covariate-adjusted sensitivity analyses based on material baseline

differences between them. For this purpose, we will consider variables with standardized differences exceeding 15% and/or variance ratios exceeding 2.0 for inclusion in these models. Any adjustments for continuous covariates will include linear as well as nonlinear representations of these variables using restricted cubic spline terms. To assess sensitivity to the imputation models, we will also compare results of analyses using multiply-imputed data with results based on complete cases and available cases and, for any outcomes with borderline results, to those from alternative imputation models. To assess sensitivity to the choice of data transformations and distributional assumptions, we will compare results to those of multinomial based categorical data mixed models for marginal mean scores.

Exploratory/descriptive outcomes

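### As most naturally read, the treatment-effect model lets the two arms' baseline means differ; a common baseline mean would usually give a narrower interval from the same data.

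*SAP*

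**What the plan says.** - **Form of the models.** In Outcome description and distributional assessment, the SAP says it will "fit preliminary mixed models with fixed effects of randomized treatment, visit, and their interactions, and with unrestricted covariance matrices". It adds that "These models will not be used to estimate treatment effects"; they serve only to check residuals. The same section names baseline, six months and twelve months as the observations to be analysed, so baseline is a response.
- **Inferential model.** Treatment effect estimation and testing says: "Treatment effects will then be estimated and tested by fitting mixed models, also as described above, on the original or transformed scale". The only stated changes from the models above are equally spaced visits and linear time. The effect is the difference between arms in annual rate of change, combined over imputations.
- **Covariance.** Six structures are compared. "The homogeneous AR(1) will be considered the default if it yields close to the minimum BIC"; otherwise the structure with the smallest BIC is used.
- **Baseline imbalance.** In Sensitivity analyses the SAP relies on randomisation for the planned analyses and offers covariate adjustment only as a sensitivity analysis: "we will consider variables with standardized differences exceeding 15% and/or variance ratios exceeding 2.0 for inclusion in these models". It is unclear whether the baseline outcome is among the eligible variables.
- **Timing of baseline.** The protocol (Participant Recruitment, Screening and Randomization) gives the total participation time as "including ~2.5 weeks for cycle delivery and completion of initial Comprehensive Assessments (On-/Off- meds". The SAP's descriptive analysis set is "all randomized patients who complete baseline procedures for initiating randomized treatment and follow-up, and for whom study follow-up is initiated". Neither says plainly that the baseline outcomes precede allocation.

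**The concern.** Carrying "fixed effects of randomized treatment, visit, and their interactions" over to linear time leaves a treatment main effect in the model. With time zero at baseline, that term is a free difference in baseline means. Randomisation makes its expected value zero if baseline precedes allocation, so estimating it usually costs precision in the slope difference. The baseline data are not ignored: they are modelled, and they enter the imputation. What goes unused is the equality of the two baseline means.

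Nothing else in the SAP restores it. No passage drops the treatment main effect or adjusts the primary model for baseline, and an imbalance-triggered sensitivity analysis does not change the primary test. That test gates every claim of benefit, and the eight secondary outcomes follow the same approach, so lost precision carries through the whole hierarchy.

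**Working it through.** The plan states no power, effect size, SD, correlation or dropout rate, so it has no figure to reproduce. The check compares the two mean models under stated assumptions.

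**Inputs.** From the documents: visits at 0, 0.5 and 1 year, linear time, 1:1 allocation, two-sided 5%, AR(1) as default covariance. Assumed: baseline-to-month-12 correlation r from 0.5 to 0.9, SDs constant or growing, and complete data.

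**Formulas.** For one arm let V = (X′S⁻¹X)⁻¹, with X holding an intercept (a) and time (b), and S the 3 × 3 covariance matrix. Apart from the common factor 2/n:

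- separate baseline means: variance of the slope difference = V_bb
- common baseline mean: variance = V_bb − V_ab²/V_aa
- ratio = 1 − V_ab²/(V_aa·V_bb) = 1 − corr(a, b)², which cannot exceed 1 for a given covariance

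**Example: AR(1), r = 0.7, constant variance.** V_aa = 0.999, V_ab = −0.3, V_bb = 0.6. Ratio = 1 − 0.09/(0.999 × 0.6) = 0.850. The interval is 1 − √0.850 = 7.8% narrower. If the planned comparison had 80% power, the new power is Φ((1.960 + 0.842)/√0.850 − 1.960) = 86%.

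**What the planned model estimates.** Under homogeneous AR(1) or compound symmetry (CS), the separate-means slope weights on the three visits are exactly (−1, 0, 1). The planned effect on completed data is then the unadjusted difference in month-12 change. With heterogeneous variances this is approximate: for SDs 1, 1.1, 1.2 and r = 0.7 the AR(1) weights are (−1.083, 0.167, 0.917).

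**Constant variance**

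| r | AR(1) ratio | Interval narrower, AR(1) | 80% power becomes, AR(1) | CS ratio |
|---|---|---|---|---|
| 0.5 | 0.749 | 13.5% | 90% | 0.727 |
| 0.6 | 0.799 | 10.6% | 88% | 0.786 |
| 0.7 | 0.850 | 7.8% | 86% | 0.842 |
| 0.8 | 0.900 | 5.1% | 84% | 0.897 |
| 0.9 | 0.950 | 2.5% | 82% | 0.949 |

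**Growing variance, variance ratio**

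| SDs | Structure | r = 0.7 | r = 0.8 | r = 0.9 |
|---|---|---|---|---|
| 1, 1.05, 1.1 | heterogeneous AR(1) | 0.920 | 0.968 | 1.000 |
| 1, 1.05, 1.1 | heterogeneous CS | 0.910 | 0.963 | 0.999 |
| 1, 1.1, 1.2 | heterogeneous AR(1) | 0.966 | 0.997 | 0.977 |
| 1, 1.1, 1.2 | heterogeneous CS | 0.956 | 0.995 | 0.980 |

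**Dropout.** With an assumed 20% dropout and AR(1), a baseline-to-month-6 correlation of 0.8 (r = 0.8² = 0.64) gives intervals 8.2% narrower, against 9.5% with complete data.

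**Sensitivity to non-linear effects.** At r = 0.7 with constant variance, the common-mean weights are (−0.711, 0.023, 0.989) under AR(1) and (−0.737, 0.105, 0.947) under CS. An effect fully present by month 6 is estimated at 0.023 + 0.989 = 1.01 (AR(1)) or 0.105 + 0.947 = 1.05 (CS) times the month-12 difference. An effect appearing only after month 6 is estimated at 0.99 or 0.95 times.

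**ANCOVA of month 12 on baseline.** With constant variance its ratio to the planned variance is (1 − r²)/(2(1 − r)) = (1 + r)/2, or 0.75 to 0.95. With SDs 1, 1.1, 1.2 and r = 0.8 to 0.85 it is 1.005 to 1.009, slightly worse than planned.

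**Simulation.** Under the null with known AR(1) covariance, 125 per arm, r = 0.6 to 0.8 and 40,000 replicates, type I error was 0.048 to 0.051 for both models. With AR(1) estimated by REML (1,000 trials at each of three month-6 correlations: 0.6, 0.8 and 0.9), the common-mean standard error was smaller in every trial and coverage was 94.2% to 95.4%.

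**The case against.** The case for leaving the plan alone has several parts.

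- **No error.** Both models are standard, and the planned one is valid. True; this is a point about precision only.
- **The model is inferred.** The fixed effects are not listed, and the published design paper that the SAP cites was not available. The SAP also reports back-transformed effects for participants with the same starting value, but that governs reporting rather than the fitted model. The hedge stands: this is the natural reading.
- **Baseline may follow allocation.** The timing is unclear, the on- and off-medication examinations are randomly ordered, and participants would know their arm. If effort at the baseline tests could depend on arm, imposing equal means could introduce bias. This stands as a condition on the fix.
- **The gain may be negligible.** With growing variance and high correlation it is. This stands as a limit on size.
- **Late effects are attenuated, and non-linearity is examined only for significant outcomes.** The worst constant-variance case here is CS at r = 0.5, where an effect appearing only after month 6 is estimated at 0.909 of its month-12 value. The standard error shrinks by more: 0.909/√0.727 = 1.07, so the expected test statistic still rises.
- **Arm-specific rates borrow baseline information across arms.** The borrowed weight is 0.10 at r = 0.8 and 0.24 at r = 0.5 (AR(1), constant variance). These rates remain unbiased under randomisation, and the separate-means model can still supply each arm's own change.
- **Quantile or multinomial fallbacks do not take this specification directly.** True, but they apply only to outcomes that leave the default model.

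**Conclusion.** The concern holds as an avoidable loss of precision; the planned test's validity is not in question. On the natural reading, the model estimates a baseline difference that randomisation makes zero in expectation. With constant variance and r between 0.5 and 0.9, the common-mean model has 0.73 to 0.95 of the planned variance across AR(1) and CS. With growing variance the advantage shrinks and can vanish. For a known covariance it is never worse.

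The size for this trial cannot be fixed, because the documents give neither SDs nor correlations. The conclusion rests on the linear-time model carrying over the treatment main effect, and the remedy rests on baseline being unaffected by allocation. The change is worth making because the primary test gates all claims, but confidence in a material gain is only moderate.

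**What to change.** 1. In Treatment effect estimation and testing, write out the fixed effects of the inferential model, including whether site is a term. This is needed whichever mean model is chosen.
2. State whether the off-medication baseline outcomes are measured before allocation or, if not, why allocation cannot affect them.
3. If that condition is met, prespecify a common intercept, linear time and treatment × time, with no treatment main effect, for the primary and eight secondary outcomes analysed by the linear mixed model. Do this before outcomes are compared by arm.
4. Keep the separate-means model as a sensitivity analysis and as the source of each arm's own rate of change.

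ANCOVA of month 12 on the baseline outcome is an alternative. The common-mean model is preferable because it keeps the rate-difference estimand of the SAP Overview and does not lose precision in the growing-variance cases.

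The cost is a few lines of SAP text and code and no new data, plus a note of any departure from the published plan if that plan specifies otherwise. It also means accepting a small sensitivity to non-linear effects, which the SAP already plans to examine for significant outcomes.

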
Aim 1: To determine the disease-altering effects of a home-based high-intensity aerobic exercise program.

12-month MDS-UPDRS III rate of decline while off medication will serve as the primary outcome.

Hypothesis: Those in the high intensity exercise group will have a significantly smaller one-year rate of decline in MDS-UPDRS III scores compared to the UCC group.

Aim 2: To determine the effects of a home-based aerobic exercise program on upper and lower extremity function using biomechanical outcomes.

Our Nine Hole Peg Test (9HPT),¹⁹ gait speed¹⁹ and Timed Up and Go (iTUG)^{20,21} iPad modules will be used to quantify upper and lower extremity function.

Hypothesis: Performance on 9HPT, gait speed and iTUG will show significantly slower rates of decay over 12 months for those in the exercise group compared to the UCC group.

Aim 3: To determine the effects of a home-based aerobic exercise program on non-motor function.

Non-motor assessments will be evaluated using our iPad-based tests of processing speed (Processing Speed Test^{19,22}), working memory and set switching (Trail Making Test A & B).

Hypothesis: Rates of decline in executive functions from enrollment to 12 months will be significantly less in the exercise group compared to the UCC group.

Aim 4: To develop a prognostic model to predict 12-month MDS-UPDRS III decline for patients participating in a home-based high-intensity aerobic exercise program.

PD demographics (age, gender, disease duration, primary symptoms, age of onset, etc.) coupled with exercise performance variables (compliance, duration, cadence, heart rate, power, heart rate variability) will be used to predict 12-month change in MDS-UPDRS III scores among the exercise cohort.

Hypothesis: Demographics, baseline PD status and comorbidities, and exercise performance will predict 12-month PD progression. Time in target heart rate zone and cadence, particularly, will notably improve predictions over those from baseline measures only.

APPROACH

To test the hypothesis that high intensity exercise completed by PD patients in their the home can alter disease progression, we will consent and randomize approximately 250 CC and UU PD patients to home-based high-intensity aerobic exercise or UCC within 3 years, and monitor group exercise parameters, activity levels, and PD progression in both groups. The trial will be conducted under Data Safety Monitoring Board (DSMB) oversight.

[figure not shown]

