To control the overall false positive rate of claiming disease-modifying therapeutic benefit from the home Peloton-based aerobic exercise program at 5% in the context of CYCLE II's nine inferential and other descriptive/exploratory outcomes, interpretation of significance testing will be in accordance with a prespecified outcome hierarchy. Specifically,

- i. overall benefit will only be claimed if the test of the primary UPDRS III outcome is statistically significant in the direction of exercise superiority at a two-sided $\alpha=5\%$,
- ii. benefit will only be claimed for a secondary motor inferential outcome if i) is satisfied and if the treatment effect is also statistically significant for that secondary motor outcome after Holm-Bonferroni adjustment for multiple testing of the five secondary motor outcomes; and
- iii. benefit will only be claimed for a secondary non-motor inferential outcome if i) is satisfied and if the treatment effect is also statistically significant for that secondary non-motor outcome after Holm-Bonferroni adjustment for multiple testing of the three secondary non-motor outcomes;
- iv. benefit will not be claimed to have been demonstrated based on estimated treatment effects on any variable other than the nine prespecified primary and secondary endpoints, and any associated p-values and confidence intervals for such other variables will be presented as descriptive only and potentially for guidance by designers of subsequent studies, and specifically noted to be unadjusted for multiple comparisons of over a dozen outcomes.

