In general, these variables will be described and modeled similarly to secondary outcomes, to potentially support future research. Hypothesis testing results, if obtained, will be interpreted descriptively and not to claim benefit or harm on the basis of CYCLE II data. The distributions of patient-reported falls within the course of the study year across patients within each treatment group will be assessed for compatibility with Poisson distribution. If, as is anticipated, overdispersion is observed, then the negative binomial or other models for overdispersed count data will be entertained.

Adverse events

Adverse events will be descriptively tabulated and compared by Common Terminology Criteria for Adverse Events (CTCAE) system/organ class and preferred term. Serious adverse events will be similarly tabulated and described in individual listings including calendar date and interval from randomization, severity grade (1-5), current status, and assessed relatedness to the exercise intervention. Serious adverse events related to the intervention are expected to be few, and formal hypothesis testing will not be performed due to anticipated low statistical power and the multiple testing context.

Effect modification/subgroup analyses

For those outcomes for which a statistically significant effect of the intervention is found, we will examine statistical interactions of the randomized aerobic exercise regimen with study site, age, sex, BMI, employment status, patient-reported intensity of regular pre-study exercise, primary Parkinson's disease symptoms, primary Parkinson's disease symptom, years since Parkinson's disease diagnosis, whether or not the patient reports any falls during the pre-study year, and baseline MDS-UPDRS III value. For potential categorical effect modifiers, we will focus on an overall Wald test rather than p-values for comparisons of specific subgroups. For continuous variables, we will focus on linear interactions. If a linear interaction is detected, however, we will also assess possible nonlinearity in models using restricted cubic spline effects, and we may also choose to reexpress and communicate the effect in terms of categories defined by ranges to better communicate clinical relevance.

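### Do two parallel Holm families behind one primary gate break the SAP's 5% false positive rate?

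*SAP*

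**What the plan says.** The hierarchy is in the SAP under Treatment effect estimation and testing. Its opening sentence gives the aim: "To control the overall false positive rate of claiming disease-modifying therapeutic benefit from the home Peloton-based aerobic exercise program at 5" per cent. It sets that aim in the context of "nine inferential and other descriptive/exploratory outcomes, interpretation of significance testing will be in accordance with a prespecified outcome hierarchy".

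- **Rule i (primary).** Overall benefit is claimed only if MDS-UPDRS III is "statistically significant in the direction of exercise superiority at a two-sided" alpha of 5%.
- **Rule ii (motor).** Benefit is claimed for a motor secondary only if rule i is met and the outcome is also significant "after Holm-Bonferroni adjustment for multiple testing of the five secondary motor outcomes".
- **Rule iii (non-motor).** The same condition applies, with significance judged "after Holm-Bonferroni adjustment for multiple testing of the three secondary non-motor outcomes".
- **Rule iv.** No benefit is claimed on any other variable.

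Rules ii and iii each depend on rule i and not on each other. Neither states an alpha, and neither repeats rule i's direction clause.

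Significance also triggers later work. The text after the rules says that for inferential outcomes where "statistically significant treatment effects are found, in either direction, we will further explore the nature of the treatment effect". The section on Effect modification/subgroup analyses says: "For those outcomes for which a statistically significant effect of the intervention is found, we will examine statistical interactions".

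**The concern.** One gate opens two families, each with its own Holm adjustment and, on the natural reading, each at 5%. Holm controls error within a family and not across two. Once the primary succeeds, the two family error rates add, and this is the only situation in which secondary claims are made. The opening sentence nevertheless gives a single 5% in the context of nine inferential outcomes, and rule i ties 5% to a two-sided test. A reader who takes 5% as the two-sided familywise rate over all nine would be relying on a rate that could nearly double. The follow-up modelling acts on significance in either direction, so two-sided error seems to matter in practice too. At stake is whether a secondary finding reported after a positive primary carries the protection that the SAP advertises.

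**Working it through.** **Inputs from the SAP.** The overall rate is 5% for claims of benefit. The primary is tested at two-sided 5% and counts only in favour of exercise. There are five motor and three non-motor secondaries, and both families depend on rule i alone.

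**Assumptions.** Each family runs at two-sided 5%, the only level the SAP names. The correlations, the power of the primary and the power of the secondaries are not in the documents, so ranges or assumed values are used.

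**1. The SAP's own figure: false claims of benefit.**

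- *Primary null.* Any claim needs the primary significant in favour of exercise: 0.05/2 = 2.5%. This caps all nine outcomes.
- *Primary effect real.* The primary cannot give a false claim, so only the secondaries count. Each family contributes about 0.05/2 = 2.5% in the benefit direction. The sum is 0.025 + 0.025 = 5.0%. With independent families it is 1 − 0.975² = 4.94%.

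The 5% is reproduced as an approximate ceiling.

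**2. The alarming figure: any false secondary rejection, either direction, gate open.**

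- Additive bound: 0.05 + 0.05 = 10%.
- One true null left in each family, independent: 1 − 0.95² = 9.75%.
- All eight null, independent: motor 1 − 0.99⁵ = 4.90%; non-motor 1 − (1 − 0.05/3)³ = 4.92%; together 1 − (1 − 0.0490)(1 − 0.0492) = 9.58%.
- If the gate opens with assumed probability 0.8 or 0.9, independently of the secondaries: 0.8 × 9.75 = 7.8%, or 0.9 × 9.75 = 8.8%.

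**3. Effect of correlation.** Eight normal test statistics with a common correlation were simulated, with the gate open and 400,000 replicates per setting.

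| Correlation | All eight null: either direction | All eight null: favouring exercise | One null per family: either direction | One null per family: favouring exercise |
|---|---|---|---|---|
| 0 | 9.57% | 4.92% | 9.77% | 4.95% |
| 0.3 | 8.73% | 4.34% | 9.50% | 4.73% |
| 0.6 | 6.81% | 3.39% | 8.80% | 4.40% |
| 0.9 | 3.57% | 1.80% | 7.04% | 3.51% |

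(The 9.77% is the exact 9.75% plus simulation error.) In every row about half of the two-sided figure is chance significance favouring usual care. Rules i to iii never turn that into a claim. The benefit column stays below 5% throughout.

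**4. What a redesign would cost.** Take one truly effective secondary with an assumed 80% unadjusted power, so that its mean z is 1.96 + 0.84 = 2.80. With the gate open, power at Holm's first step is Φ(2.80 − z), where z is the two-sided critical value.

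| Scheme | Motor threshold | Motor power | Non-motor threshold | Non-motor power |
|---|---|---|---|---|
| As planned | 0.05/5 = 0.01 | 59% | 0.05/3 = 0.0167 | 66% |
| One Holm over eight | 0.05/8 = 0.00625 | 53% | 0.00625 | 53% |
| 2.5% per family | 0.025/5 = 0.005 | 50% | 0.025/3 = 0.0083 | 57% |

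Either alternative would hold the two-sided rate to 5% and the benefit rate to about 2.5%, which the SAP does not promise.

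**The case for a change.** The best case for a change is that one printed 5% could mean three rates: 2.5% for a false claim on the primary, about 5% for false benefit claims on the secondaries, or up to 10% for any false secondary rejection. The benefit rate stays near 5% only if each family runs at two-sided 5%, and that is not written. An analyst who ran Holm at one-sided 5% because the claims are directional would reach 1 − 0.95² = 9.75% for false benefit claims.

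Part of this stands: the family alpha and direction are not spelled out. The text does settle them. Rule i gives two-sided 5%, rules ii and iii ask that the secondary *also* be significant, and the same section reports 95% confidence intervals. No one-sided level appears anywhere. The word *benefit* supplies the direction. The opening sentence itself says that the controlled rate concerns claims of benefit, so the third reading goes against its wording.

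The argument from either-direction follow-up does not stand. Those passages start exploration and interaction tests, and rules i to iv decide what may be claimed. The triggers mention neither the gate nor Holm, so the percentages above do not measure error there, and rewording rules ii and iii would leave the triggers as they are.

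It is true that secondary benefit claims together can carry about 5% while the primary carries 2.5%. But the SAP's figure is 5%, so 2.5% would be a standard brought in from outside.

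Nor is the lack of an order or a split an oversight. Each rule names rule i as its only condition, so the parallel structure is explicit. It broadly matches the protocol, which gives motor function its own Aim 2 and sets a separate Aim 3: "To determine the effects of a home-based aerobic exercise program on non-motor function".

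**Conclusion.** The concern does not call for a change. On the error rate that the SAP defines, false claims of benefit, the scheme gives at most 2.5% when the primary is null and at most about 5% when the primary effect is real, so the stated 5% is met. The 9.75% is correct arithmetic for a rate that the SAP does not undertake to control, and positive correlation or an uncertain gate lowers it.

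This rests on reading both families at two-sided 5% with claims only in favour of exercise, which is the reading the text supports. Writing that into rules ii and iii would be tidier but would alter no decision rule or result. Separate families are a fair trade-off: pooling or splitting would take about 6 to 13 percentage points of power from a single effective secondary (motor 59% to 53% or 50%, non-motor 66% to 53% or 57%, under the assumed 80% unadjusted power).
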